f) Transcription Audio Files and transcripts. We will use VA approved audio recording devices. Either the VA Salt Lake City (VASLC) transcription service or the VA approved vendor, Productions Transcripts Inc., will transcribe the audio files. The VASLC has a Professional Transcription Service available to VA sites and monitored by their own IRB. The PRIME Care audio recordings to be transcribed will be labeled by the provider's unique code and saved behind the VA Firewall in PRIME Care's secure shared project folder on the VISN 4 MIRECC server \\oitphihsmsvm200.v04.med.va.gov\Research). If VASLC transcription staff are used they will be given access to a limited access sub-folder. Approved study staff will place a copy of the audio files in this folder for an approved VASLC transcriptionist to access for the purposes of transcription. If Productions Transcripts Inc. staff are used, the audio files will be submitted by a study team member using a login/password to https://client.productiontranscripts.com/ and stored on secure servers located at PhonixNAP, [name]. The transcriptionist will transcribe each interview verbatim and, depending on the vendor, either save the completed transcript in the sub-folder, or make available for download through the secure website. As completed transcripts become available, final versions will be stored on the VISN 4 MIRECC server (\\oitphihsmsvm200.v04.med.va.gov\Research) in a folder accessible by study staff only. Final transcripts are coded and will only be identified by the provider ID; any identifying information will be removed before analysis. For data analysis, temporary copies of the transcripts will be used on local servers at the Buffalo and Boston VAMCs as well as the University of Buffalo. Analytic staff at these three sites may print temporary hardcopy transcripts for qualitative analysis. When not in use these hard copy transcripts will be kept in locked file cabinets and at the end of the study will be securely discarded.

5.6 Data Analysis

Prior to data analysis, it will be necessary to create appropriate databases by combining data from BHL, CDW, and REDCap, de-identified to remove all personal or identifying information (i.e., all fields with PHI or identifiers will be removed), and kept in separate password-protected files on the VISN 4 Mental Illness, Research, Education and Clinical Center (MIRECC) server space within the VA firewall. We will merge this file with the randomization assignment database (Palo Alto Cooperative Studies database). Only this resultant data file will be used in subsequent data management and analyses, and only the Principal Investigator and research staff will have access to the data. No data will be allowed outside of the VA intranet unless by agreement to make public a de-identified analytic data set.

Data Analyses. Prior to analyses, we will compare groups on a set of characteristics to check that the randomization procedure yielded approximately balanced groups. Our primary analyses will adjust for the design variables of site and provider, using fixed and random effects, respectively. If some characteristics show marked imbalance, we will perform sensitivity

analyses adjusting for them, and compare and report both sets of results. The expected distributions of our responses fall within the generalized linear models family, and we anticipate that parametric models will provide adequate fit in all cases. In all analyses, we will use standard model-checking procedures to assess the validity of our models, based on residual analyses. We will examine numerical measures of fit and graphical tests of various departures from the model based on residuals. In the event that these models provide a questionable or inadequate fit, the sample is large enough to allow sensitivity analyses via non-parametric analogues of the primary models.

5.6.a Patient response to treatment (Hypothesis #1). The primary outcome measures will be a set of binary indicators of remission (PHQ-9 score \leq 5) across the intervention phase time points (weeks 4, 8, 12, 18 and 24). We will use a mixed effects logistic regression model to test the hypothesis that patients whose treatment is informed by the PGx results are more likely to be in remission than those receiving usual care. The model will have a binary indicator from the intervention group as the main explanatory variable, together with variables for time and group by time effects. The model will also include a fixed effect for site. The covariance structure of the model will take the hierarchical structure of the design into account, to accommodate nesting of repeated measures within patients, and nesting of patients within providers. Including a random intercept for provider, and correlated residuals within patient, should account for the nesting, but we will use information criteria to compare the fit of different covariance structures to ensure adequate fit. As there is particular interest in the remission rate of patients at the end of treatment, we will report a model-based comparison between the groups at the endpoint of the intervention phase.

To examine the effects of patient-level and provider-level characteristics, we will include these variables and their interactions with intervention group in the logistic regression model. For example, we will examine the effects of sex, race and ethnicity, baseline depression severity, the number of prior treatment episodes, and the effects of primary care versus specialty care, etc. We will also test for heterogeneity of the intervention effect across sites (i.e., site by treatment interactions). Analyses to assess the influence of missing data, and of adherence at the provider and patient level, are described below. Our reports will include clear descriptions of the statistical methods used and the clinical interpretations of the parameters used to test the hypotheses, with estimates, standard errors, confidence intervals and *p*-values associated with the parameters.

5.6.b. Patient and provider use of PGx results (Hypothesis #2). For each provider-patient dyad in the trial, we will use the results of the genetic test to classify each medication prescribed by the provider to that patient as green, yellow, or red, thus creating an ordinal measure for each time the provider prescribes a medication. Our primary response for Hypothesis #2 will be the correspondence between the study-period prescription for the provider-patient dyad across the randomized groups. We will compare the groups on the probability of receiving medications of the three types (red, yellow, green) using mixed effects ordinal regression model, including random intercepts for providers.

5.6.c. Secondary Responses (Hypothesis #3). We will use generalized linear regression models to evaluate secondary outcomes, using the same covariates as above: a binary indicator for intervention group, and variables for site, provider, and depression severity. Regression models will include random effects to accommodate correlations due to repeated measures and nesting of patients within providers.

Secondary analyses will include an examination of the longitudinal trajectories of PHQ-9 summaries of depression severity across the intervention phase. These models will use the overall PHQ-9 score as a response, yielding a set of continuous (possibly skewed) repeated measures. These responses will be analyzed using mixed-effects linear models (or mixed-effects gamma models, depending on the degree of skewness). We will compare the groups on functional improvement, using the mental health component of the VR-12 score, with analogous generalized linear mixed effects models appropriate to the response distribution.

We will compare the groups on the rates of side effects that are moderate or severe. Indeed, side effects may be more plausibly related to serum antidepressant levels and thus PGx results than depressive symptoms. The data will include ordinal ratings of headache, nausea or vomiting, diarrhea, constipation, and sexual dysfunction at weeks 4, 8, 12, 18, and 24. We will use a mixed effects ordinal logistic regression model to test whether there are differences in the probabilities of moderate or severe side effects between the two intervention groups. We will compare the two groups on the number of outpatient visits per patient using a regression model for count outcomes, with a random intercept for provider to accommodate nesting pf patients within providers. We expect that a negative binomial, possibly with zero-inflation, will provide the best fit to the response distribution. We will also consider the delay in treatment in the intervention group as a potential adverse outcome if it leads to more patients not receiving treatment.

Actigraphy will be used in secondary analyses, as an objective measure of response to depression treatment. While there will not be a true baseline period of assessment (pretreatment) we will utilize the first 2 weeks of study participation as a marker of baseline activity. This is consistent with depression treatment typically taking 4-6 weeks to see objective improvements. We will then examine change in daytime activity (exercise and energy expenditure) as well as nighttime sleep (efficiency, awakenings) as markers of improvement. We will examine the relationship between these markers and self-reported symptoms and contrast improvement across the two arms. We will also be able to examine the degree to which sleep and activity are moderators of depression response. Finally, there are a number of other potential questions that could be examined. The availability of genetic data would also permit analyses examining associations between genomic variants and objectively-assessed sleep and activity phenotypes

5.6.c. Economic evaluation. There are a variety of methods and perspectives that can be used in health economic evaluations. For this proposal, we will use three methods (budget impact analysis (BIA), cost-effectiveness analysis (CEA), and Markov modeling) and one perspective (VA) for the economic evaluation of the clinical trial. BIA has become essential for developing the business case for healthcare interventions generally and health technology interventions in particular. CEA combines cost and patient outcomes into a single outcome. Markov models can use the clinical trial data to run the BIA or CEA beyond the 24-week duration of the PGx trial.

The economic evaluations described above will be conducted from the payer's perspective (VA) for the main analyses. VA costs will be assessed using Decision Support Systems (DSS) National Data Extracts, which use an activity-based cost allocation method; includes fixed direct, variable direct, and fixed indirect costs; and is the official cost managerial accounting system for the entire Department of VA. Cost estimates from the VA Health Economics Resource Center (HERC) will be used in a sensitivity analysis. Access to DSS and HERC data will be requested through VA Corporate data warehouse (CDW/VINCI) and National Data Systems (NDS). Outpatient costs for the main analysis will be organized in the following groups

by primary stop code field: primary care, mental health specialty care, ancillary, physical health specialty, and other (i.e., costs that fall into none of the other categories). Outpatient VA medication costs will be assessed using VA DSS data. The cost of each prescription will be based on the drug product costs and the supplies needed to dispense the prescription according to dispensing location (centralized mail order pharmacy vs. pharmacy window). PGx intervention costs will include the cost of the PGX test and additional provider time to utilize the PGx data. Other costs for setting up the communication of PGx data to providers will be considered sunk costs and not included in the economic evaluation. In secondary analyses, inpatient cost and non-VA healthcare utilization costs will be added to the main analysis cost. Non-VA healthcare utilization will be collected via patient self-report and average Medicare payment rates applied.

Budget Impact Analysis. The BIA will be conducted in accordance with the guidelines from the International Society for Pharmacoeconomics and Outcomes Research (ISPOR). The BIA covariates will be the same as those used in the primary analysis plus one-year pre-intervention healthcare utilization costs to control for baseline cost differences. Because total costs are likely to be non-normally distributed, we will use generalized linear models (GLMs) to estimate the effect of the intervention on total costs. To calculate the incremental treatment effect on costs, we will compute two predicted costs for each participant based on the coefficients from the GLM regressions and the covariate values for each patient. The first cost prediction will be for costs as if the subject had been randomized to the PGx arm of the study, and the second cost prediction will be for costs as if the participant had been randomized to usual care. The difference between these two cost predictions represents the incremental cost effect of the intervention for a particular participant because all covariate effects will be identical for the two estimates in a given patient. We will then average the difference between these two predicted values for each Veteran across all Veterans in the sample to generate an over marginal effect and 95% confidence interval. To estimate the budget impact, we will estimate the total 6-month cost that would be incurred by VA to deliver PGx tests to all VA patients who would be eligible for the PGx trial using the inclusion and exclusion rates. This number will be multiplied by the marginal cost difference calculated above. Sensitivity analyses will include using HERC cost data and cost range for PGx testing.

Cost-Effectiveness Analyses (CEA). The CEA will be conducted in accordance with the guidelines from the US Panel on Cost-Effectiveness in Health and Medicine. The CEA result will be a ratio with marginal cost in the numerator and marginal effectiveness in the denominator. The marginal cost component of the CEA will use the methods described for the BIA above. The effectiveness component of the ratio will be calculated using disease-specific (i.e., depression) and generic (i.e., quality-adjusted life year or QALY) outcomes. The diseasespecific outcomes will be measured by calculating depression-free days from the PHQ-9 scores. Depression-free days will be calculated by using a formula now used for multiple depression severity measures where a PHQ-9 score <5 is considered depression free (score=1) and a score of 15 or more is considered fully symptomatic (score=0). Scores in between will be assigned a linear proportional value. Generic QALYs will be calculated using the Veterans RAND 12-item Health Survey (VR-12) standard gamble to QALY conversion formula. Total depression free days and QALYs will be calculated using area under the curve methods. GLM methods similar to those described above for costs will be used to calculate marginal effectiveness. Typical standard error estimation methods do not apply to incremental costeffectiveness ratios for two reasons. First, the possibility of having zero or near zero denominators is non-negligible. Second, expenditure and effectiveness estimates are rarely independent. Therefore, we will use 1000 replications of a nonparametric bootstrap with replacement model to generate an empirical joint distribution of marginal (or incremental) costs

and QALYs. We will then construct acceptability curves representing the probability of falling below incremental cost-effectiveness ratio thresholds ranging from 0 to \$100 per depression free days and 0 to \$100,000 per QALY.

A Markov model will be constructed to evaluate the cost-effectiveness of the use of PGx tests beyond 6 months. The cycle length for the model will be 30 days with a time horizon of one-year. The baseline model population consists of Veterans initiating antidepressant treatment for depression. The respective ages for the baseline model population will be derived from Veterans initiating treatment for MDD in the national VA database so that findings can be generalized to all Veterans. The model structure will be adapted from the study by Perlis et al. [53], which performed cost-effectiveness analyses using a Markov model incorporating probabilities from the multicenter STAR*D effectiveness study of depression. For this study, probabilities from the current trial will be used. Patients will enter the model with a current episode of depression. The first decision node will be whether or not PGx test data are available to the prescribing clinician. Under each study arm, we will develop a state-transition model of probabilities in which an individual patient could occupy a distinct health state, depressed (on treatment consistent with PGx test or on treatment not consistent with PGx test or off treatment), well (on treatment consistent with PGx test or on treatment not consistent with PGx test or off treatment), or death. Probabilities of remission, discontinuation, and recurrence will be drawn directly from the trial and extrapolated to one year. For remitted patients ("well"), the mortality rate will be equal to the age-gender-adjusted all-cause mortality rate from the U.S. Census. For depressed patients, we will add the rate of suicide among depressed patients to the agegender-adjusted all-cause mortality rates of the remitted patients. Costs and utility values will be calculated as described in the section for BIA and CEA studies. For the base case analysis, we will simulate a hypothetical cohort of 10,000 patients using first-order Monte-Carlo simulation. The simulated cohort will have mean demographic characteristics consistent with MDD patients initiating treatment in the VA population nationally. We will perform both 1-way sensitivity analysis on the influential model input parameters (e.g., time horizon, remission, discontinuation, recurrent rates, drug cost, and cost of genomic test) and second order Monte-Carlo simulation by generating 100 cohorts of 10,000 patients to account for potential patient heterogeneity. Since the time-horizon is 1 year, no discounting will be applied.

5.6.d. Change in prescribing in delayed results group post-intervention (Hypothesis #4). At the conclusion of the six-month intervention phase of the trial, the genetic test results will be returned to the providers (and patients) in the treatment as usual group. We expect to see a rise in use of medication categorized as green medications after the results are returned. Thus, within the delayed results group, we will use a mixed effects ordinal response model to estimate and test a time dependent change in the probability of receiving medications of the three types (red, yellow, green) after the intervention. In addition, we will perform a bivariate analysis, combining the ordinal model with a linear model for the PHQ-9 score, to examine whether change in prescribing practice (i.e. increased prescribing of green-type medications) is related to change (i.e. an expected decline) in PHQ-9 scores.

5.6.e. Biological confirmation of effect of testing. As reviewed above, the literature on genetic variation affecting the pharmacodynamics of antidepressant treatment is sparse, and the available tests depend nearly completely on the variation associated with antidepressant pharmacokinetics, where individual variants have much greater effects. As part of the clinical trial we have included the collection of additional biological samples with several exploratory aims. First we will obtain genomewide association study (GWAS) data for the 2000 participants with MDD in the PRIME Care study. This will allow us to:

- 1a. Conduct a GWAS on medication response traits (daily antidepressant dose in people whose depression remits with treatment, as in the main trial: PHQ-9 score <5). We will also explore via GWAS the most common side effects observed during antidepressant treatment.
- 1b. Evaluate the relationship of Psychiatric Genomics Consortium (PGC)-derived depression polygenic risk score (PRS) to medication response.
- 1c. Develop an algorithm that takes into account not only the genetic markers in the Assurex marker panel but also those identified through GWAS (1a above) as predicting daily antidepressant dosage and other relevant health care behaviors (e.g., smoking, use of other medications) that can affect antidepressant pharmacokinetics).

We will also use GWAS and the Assurex testing results to examine intermediate phenotypes related to serum concentrations of medications and treatment response to:

- 2a. Compare GWAS and Assurex testing results against serum drug level, which could identify novel response predictors. Assuming that serum drug level mediates treatment response (an underlying assumption of all of the PGx commercial tests), this will help to identify better predictors than those currently in use. Levels will be drawn once medication dosage is stable (4 weeks from randomization).
- 2b. Conduct a GWAŠ against baseline platelet serotonin (5HT) and percentage change in serotonin level (delta5HT, an index of serotonin reuptake inhibitor bioeffect) to identify potential mediators of response.

Finally, we will compare the utility of levels of C-reactive protein (CRP), a commonly available marker of systemic inflammation, with absolute levels of mRNA for macrophage migration inhibitory factor (MIF) and interleukin 1- β (IL-1- β) as predictors of antidepressant treatment response in the PRIME Care sample.

Remaining back up samples after these analyses are complete, might be used for additional exploratory aims, rather than discarded, to further the science around health and mental health outcomes in this patient population.

• Use remaining back up cryo serum samples to identify blood markers (metabolites) that are associated with heavy alcohol use. We will use high-dimensional multivariate analyses and machine learning approaches to determine how heavy drinking impacts systemic metabolism.

5.6.f. Contextual assessment of PGx testing and impact on future implementation. An important aspect of this trial will be to learn about delivering PGx testing in clinical practice. We will imply the Consolidated Framework for Implementation Research (CFIR) to structure a formative evaluation of the implementation of PGx testing [54, 55]. This aim will include the quantitate knowledge assessment as well as the focus and individual qualitative assessment of providers. Specifically, we will focus on an exploration of the current state of knowledge and perceptions of PGx testing, and findings will be used to develop provider and patient materials that can support the uptake and implementation of PGx testing. We will focus on how provider and patient beliefs and expectations of pharmacotherapy and PGx tests affect their use of the results (moderating the effects of Hypothesis #2). We anticipate that we will have sufficient diversity of sites represented to use qualitative methods to explore contextual factors within the CFIR domains of Inner and Outer Settings that will be important in preparing for a national rollout of PGx testing. We are particularly interested in the Inner Setting context of team care (PCMHI in PACT and BHIP in specialty Mental Health [MH] settings) as it relates to the ability of individual providers to make this change in their practice.

To accomplish these aims, we will recruit a subset of sites to participate in virtual (telephone/Lync-based) focus group interviews. We will conduct up to ten 45-minute-long (15 minute presentation, 30 minute discussion) focus groups with 3-5 prescribers each, grouped by

provider type (PCPs and psychiatrists (and other specialty mental health providers)). Membership will mirror the intended eligibility for provider participants in the trial. While these groups are smaller than typical focus groups, we believe that our highly educated participants will provide rich feedback and increase the feasibility of both provider and patient recruitment by helping us to understand the common perceptions of PGx testing. These focus groups will receive a brief presentation on PGx' s, including a sample report of Assurex results, and will then discuss current knowledge and perceptions of PGx testing. They will provide input that will facilitate the RCT (e.g., How can we help prescribers recruit for the trial? What information is needed to understand and use PGx results?), and feedback on how PGx results should be returned to providers and patients. The use of focus groups at this stage is important to enable group discussion to flesh out perceptions and stimulate ideas about how PGx testing can be implemented. All groups will be held virtually via Lync On-Line Meetings so that slides can be presented.

Finally, individual interviews with providers in the RCT will be used to identify barriers and facilitators to individual uptake and use of PGx test recommendations. We will sample across sites and providers based on the providers rate of referral and their specialty area (primary care or psychiatry) to interview up to 85 providers. Each individual interview will take 30-45 minutes and be recorded and professionally transcribed. Atlas-ti software will be used to facilitate qualitative content analysis of interview transcripts.

5.6.g. Dropout and Missing Data. At the time of enrollment, we will stress to all patients the importance of follow-up assessments, independent of treatment adherence. Despite every attempt to obtain outcome data for all patients, including those who drop out of treatment, we anticipate that there will be dropout from the study as well as intermittent missing data. To assess the sensitivity of our conclusions to missing data, we will use observed data such as baseline characteristics, intervention group, and responses obtained prior to dropout, to perform further sets of analyses. The mixed effects models described above can make use of all available responses, can accommodate the heterogeneity of response times caused by intermittent missing data, and will provide valid estimates and hypothesis tests under an assumption of "ignorable missingness," meaning that the occurrence of dropout and missing data can be predicted based on observed data. We will use extensions of these models (inverse probability weighted selection models and pattern mixture models) to examine the plausibility of the ignorable missingness assumption [56]. We will perform these analyses under a range of different prediction models and assess the sensitivity of the results.

5.6.h. Adherence. For Hypothesis #1, there are two levels of adherence to be considered. First, a provider/patient dyad in the intervention group may not use a recommended medication (this is the focus of Hypothesis #2 above) and, secondly, a patient may not actually take the medication as prescribed. We will assess adherence at the provider/patient dyad level by comparing the prescriptions that are written to the recommendations of the PGx report. We will also ascertain self-reported adherence at each assessment and will supplement with prescription data. Adherence to medication is well chronicled as an important concept in the effectiveness of treatment, yet no gold standard exists for the measurement of adherence [57, 58]. Each method has advantages and limitations. The advantage in this trial of using pharmacy records is the convenience of collection and the lack of interference with clinical practice, as this is not a standard trial with a high number of data collection time points. We will assess patients' adherence to their prescribed medication via self-report at each assessment.

To assess the sensitivity of the results of the analyses described above to non-adherence, the models described above for primary and secondary outcomes will be extended using

instrumental variable approaches. Here, the instrumental variable is randomization that, under some conditions, will control for unmeasured bias (due to self-selection to adhere or not) when estimating the relative effects of the medications in those who adhere to their assigned medication. Results will use data from all patients who show various degrees of adherence as measured by the availability of medication or adherence to the PGx recommendation and will yield estimates of the intervention effects that would have been seen in a study with full adherence. For a single overall measure of adherence, we will use the methods of Nagelkerke et al. [59]; if there is sufficient within-patient variation across time in adherence, we will use the longitudinal methods of Small et al. [60]. Because adherence adjustments tend to be small and do not have a large influence on treatment comparisons, we view these as sensitivity analyses, whose main purpose is to check that estimates of effect from the primary models can be reported without explicit adjustments for adherence.

5.6.i. Adequacy of sample size. The single primary outcome is a set of repeated binary indicators of remission from depression. As we have a single outcome, we use a Type 1 error rate of 5%. Although we expect the intervention arm to be no less efficacious than the delayed results arm, we use a two-sided test. We also assume a 20% loss to dropout, distributed evenly over time, and across the two groups. The parameters that determine power are the base rate, which is the rate of treatment success expected in the delayed results arm, and the treatment effect. The anticipated remission rate in usual care is based on results from STAR*D [19]. For the base rate, we consider rates of 20-25-30-35%, and for the treatment effect, we look at effects of 5-6-7%. The study design has patients nested within providers, so it is possible that there will be small correlations between the results for two patients of the same provider. Accounting for nesting within provider should also address the nesting within sites [61]. Our design will have approximately 200 providers, with an average of ten patients per provider. The design effect due to provider is then 1+9*r, where r is our assumed provider intra-class correlation. Our sample of size 2000 is then equivalent to an "independent patients" sample of 2000/(1+9*r). We anticipate a low ICC, on the order of r<0.05. If we assume that r=0.05, then the design effect is 1.45, and the effective sample is 1379. For a base rate of 30%, and an assumed within-patient correlation of 0.4 or lower in a compound symmetry structure, then we have 82% power for a 5% treatment effect and 92% for the same effect in an ar(1) structure, with higher power for the same 5% effect with lower base rates. For r=0.01, where we have an effective sample size of 1835, we have power in excess of 90% for 5% effects, under either covariance structure. Even with a conservative estimate of r=0.1, the design effect is 1.9, yielding more than 80% power for treatment effects of 6% or greater.

5.6.j. Data management staffing. [name] and his staff will be responsible to coordinate the various data collection methods used in the clinical trial, and will provide support to the investigators, including site principal investigators to support additional exploratory hypotheses. In this section, we describe the methods that we will use to collect, store, and distribute data from the trial.

5.6.k. Security Awareness and Training. Security awareness starts with a request by an investigator to obtain access for his or her study personnel. To gain access to the BHL and REDCap systems, a user must first attend and pass the training/hands-on certification process. The training consists of a thorough introduction to the two systems and the policies governing their use.

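### The budget impact step multiplies a total testing cost by a per-patient cost difference, so as written it does not yield a dollar budget

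*Protocol*

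**What the plan says.** The rule is in Protocol section 5.6.c (Economic evaluation), under Budget Impact Analysis. It has three parts.

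- **The model.** For costs, "we will use generalized linear models (GLMs) to estimate the effect of the intervention on total costs". Each participant gets two predicted costs, one as if assigned to PGx and one as if assigned to usual care.
- **The marginal cost difference.** "We will then average the difference between these two predicted values for each Veteran across all Veterans in the sample". A 95% confidence interval accompanies the average.
- **The scaling to VA.** "we will estimate the total 6-month cost that would be incurred by VA to deliver PGx tests to all VA patients". Only patients whom the trial would admit are meant, as defined by the inclusion and exclusion rates. The next sentence is: "This number will be multiplied by the marginal cost difference calculated above".

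Two neighbouring statements bear on the rule. The opening of the Economic evaluation section says: "PGx intervention costs will include the cost of the PGX test and additional provider time to utilize the PGx data". The Budget Impact paragraph ends: "Sensitivity analyses will include using HERC cost data and cost range for PGx testing". The SAP contains no budget impact analysis, so the protocol paragraph is the only statement of the rule.

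**The concern.** The only quantity that the scaling sentence says will be estimated is a total cost. The sentence after it multiplies that number by another money amount. A budget impact should be a number of patients times a cost per patient; the written rule has a cost in both places and a patient count in neither.

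An analyst would notice this and repair it. The practical problem is that the repair would be unplanned, made when results may already be known, and the text allows more than one. The protocol presents budget impact analysis as central to the business case for a health intervention, taken from the VA's perspective as payer, so the formula should be fixed in advance. The planned sensitivity analysis over a range of test prices has the same weakness, because it needs a clear statement of where the test price enters.

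**Working it through.** The documents state no budget impact figure, so there is nothing to reproduce. The check is one of units.

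**Inputs**

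- N: number of eligible VA patients. Not given. The Background figure of more than 300,000 counts Veterans with depression on an antidepressant, not patients meeting the trial's entry criteria.
- c: cost per patient of the test and added provider time, in dollars. Not given.
- s: change per patient in all other VA costs, in dollars. Not given.
- d: marginal cost difference, in dollars per patient, defined in the Budget Impact paragraph.

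**Step 1: units of the rule.** The first factor, the total cost of delivering tests to everyone eligible, is N × c in dollars. The second is d in dollars per patient.

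- As written: (N × c) × d, in dollars squared per patient.
- Dimensionally consistent: N × d, in dollars.

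**Step 2: confirmation by changing the currency unit.** Take assumed values, used only to test the units: N = 100,000, c = $2,000, d = $1,000.

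| Rule | In dollars | In thousands of dollars | Change |
|---|---|---|---|
| (N × c) × d | 200,000,000,000 | 200,000 | 1,000,000-fold |
| N × d | 100,000,000 | 100,000 | 1,000-fold |

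A true money amount changes 1,000-fold, and only N × d does. The ratio of the two rules is 2,000 in dollars but 200,000 / 100,000 = 2 in thousands of dollars, so it is not a measure of error.

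**Step 3: where the test cost enters.** The answer depends on whether the modelled total costs include c.

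- If they do, d = c + s. Then N × d = N × (c + s), with the test cost counted once. Adding testing cost to the scaled difference would give N × c + N × (c + s) = 2 × N × c + N × s, which counts it twice.
- If they do not, d = s. Then N × d = N × s leaves the test cost out, and N × c must be added once to reach N × (c + s).

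A wrong choice misstates the budget by N × c in either case. With assumed N = 100,000 and c from $500 to $2,000, that is $50 million to $200 million. This range shows why the point should be stated; it is not an estimate for VA.

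**Step 4: reach.** For the cost-effectiveness analysis the plan says: "The marginal cost component of the CEA will use the methods described for the BIA above". What carries over is the per-patient marginal cost, which is the numerator of its ratio. The multiplication to the VA population is not used there. Hypotheses 1-4 contain no budget impact outcome.

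**The case against.** The strongest defence is that this is a drafting slip. Inclusion and exclusion rates lead naturally to a count of patients, and the next sentence speaks of a number, so the authors very probably meant eligible patients times the marginal difference. A result in squared dollars would also be conspicuous before it was reported. As an account of intent this is persuasive, and the proposed wording adopts it. It does not remove the point: the sentence names a total cost, no other passage corrects it, and a planned formula that is wrong as written should be corrected.

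The defence is also right about three stronger readings that a reader might infer.

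- *That the result is too large by a factor equal to the test price.* A squared-dollar quantity has no unit-free ratio to a dollar budget, and the documents give no price.
- *That the test cost is counted twice.* In a product it would enter both factors, which is not a doubling. Even that requires the modelled total costs to include the test. This is the natural reading of the Economic evaluation section, but the Budget Impact paragraph does not say it.
- *That a coverage decision rests on this figure.* The documents link budget impact analysis to the business case and mention no coverage decision based on it.

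**Conclusion.** The point holds as an error in a stated formula. The budget impact step multiplies dollars by dollars per patient and cannot give a valid budget as written. This follows from the text alone and needs no assumed figure.

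No numerical size should be attached to it, because the eligible count, test price and marginal cost are all absent from the documents. Whether the modelled total costs include the test and provider time is a separate ambiguity, to be settled by a statement from the authors.

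The scope is narrow: the last step of one economic analysis that lies outside Hypotheses 1-4. The per-patient marginal difference and its confidence interval are defined in coherent units, and the cost-effectiveness analysis does not use the faulty step.

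**What to change.** Replace the scaling rule with wording to this effect:

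*The number of VA patients meeting the trial's entry criteria will be estimated from the inclusion and exclusion rates. The 6-month budget impact will be this number times the marginal cost difference per patient.*

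Then add one statement on the test cost: the PGx intervention costs (test and added provider time) are part of the total costs modelled by the GLM for the PGx arm, and so enter once through the marginal difference. If the authors intend the GLM to exclude them, the text should say so and add them once per eligible patient. The sensitivity analysis on test price should vary the cost at that same single place.

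The cost is one replaced rule and one added sentence in the protocol. No data collection, sample size or primary analysis changes. Ideally the wording is settled before the cost data are analysed.
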